3.6. Number of Patients

This is an event-driven trial: It is expected that a minimum of approximately 1612 primary endpoint events will be required during the study. A total of approximately 7990 patients will be entered into the study to either receive AMR101 or placebo (approximately 3995 patients per treatment group) in order to observe an estimated 1612 events that make up the primary composite endpoint for efficacy. Additional patients may be enrolled beyond the projected 7990 if the number of events contributing to the primary endpoint appears less than, and inconsistent with, projections (see [Section 12.3](#)).

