3.2 Study Design

This is a Phase 3b, multi-center, multi-national, prospective, randomized, double-blind, placebo-controlled, parallel-group study.

This is an event driven trial comparing the effect of AMR101 vs. control, in terms of the composite endpoint listed above as the primary efficacy endpoint. The study has been planned to accrue a total of 1612 efficacy endpoint events with two planned interim analyses when approximately 967 (60%) and 1290 (80%) of the events have occurred and been adjudicated. The study includes patients with established CVD (CV Risk Category 1) and patients ≥ 50 years old with diabetes and at least one additional risk factor for CVD but with CVD not established (CV Risk Category 2).

Sample size calculation was based on assumptions of constant hazard, asymmetric recruitment rate over time and without factoring for dropouts. A risk reduction corresponding to a hazard ratio of 0.85 (AMR101 vs. control) is assumed. 1612 events would be required to detect this hazard ratio with approximately 90% power with one-sided alpha-level at 2.5% and with two interim analyses.

The recruitment period is assumed to be approximately 4.2 years with 20% recruitment in the first year, 40% in the second year, 20% in the third year, 19% in the fourth year and the remaining 1% in the last 0.2 years. The expected maximum study duration is estimated at 6.5 years unless the trial is terminated early for efficacy or safety issues. A one-year event rate of 5.2% (hazard = 0.053) in the control arm is also assumed. Under these assumptions the number of patients to be enrolled is $N = 7990$.

Randomized treatment assignment to either 4 g/day AMR101 or placebo in a 1:1 ratio will be provided using the internet via an interactive web response system (IWRS). Randomization will be stratified by CV Risk Category 1 or 2 (defined in the inclusion criteria of the study protocol), use of ezetimibe, and by geographical region (Westernized, Eastern European, and Asia Pacific countries).

Approximately 70% of randomized patients will be in CV Risk Category 1, and approximately 30% of randomized patients will be in CV Risk Category 2. Enrollment of patients within a CV risk category will be stopped when the planned number of patients in that risk category is reached or, if the enrollment target is extended beyond 7990 patients (as

described in Section 4.1), then only CV Risk Category 1 will be included in further enrollment.

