4.3.3 Baseline

In general, the baseline value will be defined as the last non-missing measurement obtained prior to the dispensing drug, unless otherwise specified. If the baseline value is missing, the value obtained at the screening visit will be used as the baseline value.

Lipid, lipoprotein, and inflammatory marker baseline values will be derived variables. LDL-C may be obtained by various methods at each visit; therefore, the baseline value obtained via Preparative Ultracentrifugation will be used, unless this value is missing. If the LDL-C Preparative Ultracentrifugation value is missing, then another LDL-C value will be used, with prioritization of values obtained from LDL-C Direct measurements, followed by LDL-C derived by the Friedewald calculation (only for subjects with TG < 400 mg/dL), and finally LDL-C derived using the calculation published by Hopkins University investigators (Martin 2013). For all other lipid, lipoprotein, and inflammatory marker parameters, wherever possible, baseline will be derived as the arithmetic mean of the Visit 2 (Day 0) value and the preceding Visit 1 (or Visit 1.1) value. If only one of these values is available, the single available value will be used as baseline.

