Since the results from the analysis of the tertiary endpoints are intended to be supportive rather than pivotal evidence of drug efficacy and safety, all tertiary efficacy endpoint analysis will be considered exploratory and statistical testing will be carried out at the nominal 5% level without adjustment.

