 - Assessment of the relationship between post-baseline biomarker values and treatment effects within the primary and key secondary composite endpoints by including post-baseline biomarker values (for example, at 4 months, or at 1 year) as a covariate.

Continuous tertiary endpoints include:

- Change from baseline and percent change from baseline in fasting TG, TC, LDL-C, HDL-C, non-HDL-C, VLDL-C, apo B, hs-CRP (hsCRP and $\log[\text{hsCRP}]$), hsTnT, and RLP-C (to be estimated from standard lipid panel, $\text{RLP-C} = \text{TC} - \text{HDL-C} - \text{LDL-C}$ [Varbo 2014]) (based on ITT estimands);
- Change in body weight;
- Change in waist circumference.

The fasting lipid panel is tested at Screening (Visit 1 or Visit 1.1), Randomization visit (Visit 2; Day 0), Visit 3 (Day 120; ~4 Months) and all other follow-up visits including the last visit. For change from baseline to 1-year Preparative Ultracentrifugation measurements for LDL-C will be analysed, unless this value is missing. As described in Section 4.3.3, if the LDL-C Preparative Ultracentrifugation values is missing, then another LDL-C value will be used, with prioritization of values obtained from LDL-C Direct measurements, followed by LDL-C derived by the Friedewald calculation (only for subjects with TG < 400 mg/dL), and finally LDL-C derived using the calculation published by Hopkins University investigators (Martin 2013). In addition, change from baseline to day 120 in LDL-C utilizing Friedewald's and Hopkins methods will be analysed, using the arithmetic mean of LDL-C obtained at Visit 2 (Day 0) and the preceding Visit 1 (or Visit 1.1). If one of these values is missing, the single available LDL-C value will be used. LDL-C according to Hopkins will be calculated at each visit.

The randomization visit will be considered Baseline. If a baseline value is not available from the randomization visit, then the latest screening value will be used.

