For measurements of lipids, lipoproteins, and inflammatory markers, the change from baseline and the percent change will be summarized at each visit. Since these parameters are typically not normally distributed, the Wilcoxon rank-sum test will be used for treatment comparisons of the percent change from baseline, and medians and quartiles will be provided for each treatment group. The medians of the differences between the treatment groups and 95% CIs will be estimated with the Hodges-Lehman method. In addition, shift-tables may be generated as appropriate.

As an additional exploratory analysis, the relationship between post-baseline biomarker values and treatment effects with the primary and key secondary composite endpoints will be assessed by adding biomarker values (for example, at 4 month, or at 1 year, etc.) as time-dependent covariates in the Cox proportional hazards model. Diagnostic plots for the proportional hazards assumption will be evaluated.

Weight is measured at the screening visit and at all follow-up visits, including the last visit of the study. Waist circumference will be measured at the randomization visit (Visit 2; Day 0), Visit 5 (Day 720) and the last visit of the study. Descriptive statistics will be presented by visit and treatment group for baseline, post-treatment change from baseline, and the percent change from baseline. Analysis methods for repeated measurements will be used to compare percent change from baseline between treatments.

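### Marker effects are compared by an unstratified Wilcoxon test of percent change without covariate adjustment for baseline, so their confidence intervals are probably wider than the data require

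*Combined protocol and SAP*

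**What the plan says.** SAP 4.7.4 specifies that "the Wilcoxon rank-sum test will be used for treatment comparisons of the percent change from baseline" and that "The medians of the differences between the treatment groups and 95% CIs will be estimated with the Hodges-Lehman method". Its reason is distributional: "Since these parameters are typically not normally distributed". Protocol 12.2.4.4 has the same rule. hsTnT is listed with these markers and is given no other method. No covariate-adjusted, stratified or repeated-measures comparison is planned for any of them.

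Elsewhere the plan uses more. SAP 3.2 states that "Randomization will be stratified by CV Risk Category 1 or 2", with ezetimibe use and region as further factors, and the event analyses are stratified accordingly. Weight and waist circumference get repeated-measures methods in the same section, 4.7.4.

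Baseline is defined in two ways. For markers other than LDL-C, SAP 4.3.3 says that, where possible, "baseline will be derived as the arithmetic mean of the Visit 2 (Day 0) value" and the preceding screening value. SAP 4.7.4 says "The randomization visit will be considered Baseline". The tertiary analyses are exploratory, and "statistical testing will be carried out at the nominal 5% level without adjustment" (SAP 4.3.6).

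**The concern.** The effect of AMR101 on each marker is a stated tertiary objective, and its useful product is an estimate with a confidence interval. Non-normality is a reason for a log scale or for ranks. It is not a reason to leave out baseline as a covariate or the strata. Percent change does use baseline, as its denominator, but that fixes the baseline slope at one on the log scale. When the true slope is lower, the comparison carries baseline noise that a covariate would remove. At stake are the width of the intervals and adjustment for chance baseline imbalance.

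**Working it through.** **Inputs.** Planned size: "approximately 3995 patients per treatment group" (protocol 3.6). Earlier LDL-C result: -6.2%, p = 0.0067, with 225 patients on 4 g/day and 226 on placebo (protocol 1.2.2). The documents give no SD, correlation or power for any marker comparison, so there is no marker figure to reproduce. Every value of rho and every SD below is an assumption.

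**1. What is being tested.** For a positive marker, percent change is 100(follow-up/baseline - 1), which rises with log(follow-up/baseline). Ranks are unchanged, so the planned test is a Wilcoxon test of the log change.

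**2. Single baseline, equal SDs of 1.** Var(change) = 2(1 - rho). Var(ANCOVA) = 1 - rho². The ratio ANCOVA/change is (1 + rho)/2, so the change score loses (1 - rho)/2. With the Wilcoxon efficiency of 0.955 under normality, the loss is 1 - 0.955(1 + rho)/2.

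**3. Mean of two baseline values** (SAP 4.3.3), taking rho as the correlation between any two of the three values. The baseline variance is v = (1 + rho)/2. Var(change) = 1 + v - 2rho. Var(ANCOVA) = 1 - rho²/v. At rho = 0.6: v = 0.80, Var(change) = 0.60, Var(ANCOVA) = 0.55, loss = 1 - 0.55/0.60 = 8.3%, and 12.5% with the 0.955 factor. At rho = 0.3: v = 0.65, variances 1.05 and 0.862, loss 18%, and 22% with the factor.

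| Assumed rho | Single: change score | Single: with 0.955 | Two-value mean: change score | Two-value mean: with 0.955 |
|---|---|---|---|---|
| 0.2 | 40% | 43% | 22% | 26% |
| 0.3 | 35% | 38% | 18% | 22% |
| 0.5 | 25% | 28% | 11% | 15% |
| 0.6 | 20% | 24% | 8% | 12.5% |
| 0.7 | 15% | 19% | 6% | 10% |

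**4. Unequal SDs.** With k = SD(baseline)/SD(follow-up), the change score loses (k - rho)²/(1 + k² - 2·rho·k). The TG entry limits could make k smaller than 1: k = 0.7 gives 21%, 10% and 1.5% at rho 0.2, 0.4 and 0.6. In the other direction, k = 1.2 gives 47% at rho 0.3 and 33% at rho 0.7.

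**5. Which markers.** Appendix A schedules apo B, hs-CRP and hsTnT at Visit 2, Visit 5 and the last visit. At Visit 1, hs-CRP is drawn only as needed to determine the risk category. The single-baseline columns therefore mostly apply to these three. They also apply to LDL-C at one year, because ultracentrifugation is done at Visits 2 and 4, and to every marker if the 4.7.4 baseline definition governs.

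**6. Interval width.** The factor is 1/√information: 1/√0.8 = 1.12 and 1/√0.6 = 1.29. As an absolute illustration, take an assumed log SD of 0.4, 3995 per arm and a single baseline. The 95% half-width is about 0.021 (Wilcoxon) against 0.017 (ANCOVA) at rho 0.3, and 0.014 against 0.013 at rho 0.7.

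**7. Power.** Taking p = 0.0067 as two-sided gives z = 2.71. The scaling factor is √[(3995/2)/(1/(1/225 + 1/226))] = √(1997.5/112.7) = 4.21, so z is about 11.4. With data on half the patients it is about 8.1. Power exceeds 99.9% in both cases. Only very small effects are touched: for an assumed difference of 0.08 residual SD, power is 94.7%, 89.2% and 79.1% with 100%, 80% and 60% of the information.

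**8. Chance imbalance and strata.** The standard error of the baseline difference is √(2/3995) = 0.022 SD, so imbalance is slight. Strata would add roughly their R² on the change, assumed here at 1% to 5%.

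**The case against.** The strongest case for the plan is that the test is valid under randomization, the endpoints are exploratory, the sample is large, and both earlier sponsor trials (MARINE and ANCHOR) used the same Wilcoxon and Hodges-Lehmann method, so results stay comparable. All of this stands. It limits the importance of the point and is a reason to keep the rank analysis alongside a new one.

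A second objection is that the 0.955 factor assumes normality, whereas the SAP chose ranks because it expects non-normality. This stands in part. In simulations with assumed heavy-tailed errors, the planned test ranged from a 35% loss to a 30% gain against least-squares log ANCOVA. Against rank ANCOVA, without truncation of baseline, the loss was 52%, 38% and 20% at rho 0.2, 0.4 and 0.6, with a 6% gain at rho 0.8. Heavy tails therefore argue mainly against least squares, and against baseline adjustment only when rho is high.

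A third objection is that an ANCOVA fitted visit by visit uses observed cases just as the Wilcoxon test does. This is correct: only the repeated-measures alternative makes use of patients with some visits missing.

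Stronger readings are tempting and are not supported. A reader might infer that baseline is ignored, but it is the denominator of percent change. A reader might infer a fixed loss of 20% to 40%, but that needs a single baseline, equal SDs and a rho of 0.6 to 0.2 that the documents do not give. A reader might infer that subgroup comparisons of markers suffer most, but SAP 4.7.5 plans its subgroup analyses for the primary and key secondary endpoints.

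**Conclusion.** The point holds as a modest one about efficiency. The planned comparison leaves out a baseline covariate and strata that are already collected. The probable cost is 15% to 35% of the information with a single baseline (rho 0.7 to 0.3, equal SDs, log scale, before the Wilcoxon factor), and about 12% to 26% with a two-value mean baseline (rho 0.6 to 0.2, Wilcoxon factor included). Depending on the SD ratio and the tails, the true figure for a given marker could lie outside both ranges, and the rank test could even be the better one. It is most relevant to apo B, hs-CRP and hsTnT.

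The documents do not support the inference that a marker conclusion is at risk. For an effect like the LDL-C result in ANCHOR, power is near 100% under either method. The benefit is removal of 12% to 29% excess interval width, if 80% to 60% of the information is now used, and a small adjustment for chance imbalance. The two baseline definitions need reconciling in any case, because they change both the estimate and the size of the loss.

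**What to change.** In SAP 4.7.4, make the main marker comparison an ANCOVA, or a repeated-measures model, of log follow-up value on treatment, log baseline, CV risk category, ezetimibe use and region. Report the AMR101/placebo ratio of geometric means with its 95% CI. If no transformation is wanted, or for a marker that can be zero or negative (RLP-C is a difference), use a stratified rank ANCOVA. Keep Wilcoxon and Hodges-Lehmann as the sensitivity analysis and for comparability with the earlier trials.

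State one baseline definition for each marker and use it in both SAP 4.3.3 and 4.7.4.

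The cost is SAP wording and a little more programming, with no new data. The downside is a log-scale estimand that must be reported beside the median percent change.

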4.7.5 Exploratory Analysis of Subgroups

Analyses of the effects of patients off study drug and withdrawn from study have on primary endpoint will be performed.

Subgroup analyses of the primary and key secondary endpoints will be performed as described for the primary endpoint. For each subgroup, Kaplan-Meier estimates, the log-rank test stratified by stratification factors used at randomization (except where the subgroup is a stratification factor), and HRs and CIs from the Cox proportional hazards model as specified for the primary efficacy endpoint, will be summarized by treatment group.

The following subgroups will be explored:

Demographic Parameters:

- gender;
- age (<65 years and \geq 65 years);
- race (white and non-white, or any other subset with at least 10% of the total number of patients);
- geography (Westernized, Eastern European, and Asia Pacific countries); and

- baseline ezetimibe use (yes/no).

Disease Parameters:

- CV risk category;
- the presence/absence of diabetes at baseline; and
- renal dysfunction (estimated glomerular filtration rate [eGFR] <60 mL/min/1.73m²) using the Chronic Kidney Disease Epidemiology Collaboration (CKD-EPI) equation as follows:

$$eGFR = 141 \times \min(S_{cr}/\kappa, 1)^\alpha \times \max(S_{cr}/\kappa, 1)^{-1.209} \times 0.993^{\text{Age}} \times 1.018 \text{ [if female]} \times 1.159 \text{ [if black]}$$

Where:

S_{cr} is serum creatinine in mg/dL,
 κ is 0.7 for females and 0.9 for males,
 α is -0.329 for females and -0.411 for males,
 min indicates the minimum of S_{cr}/κ or 1, and
 max indicates the maximum of S_{cr}/κ or 1.

Treatment Parameters:

- statin intensity at baseline (statin type and regimen)

Statin intensity categories as defined in ACC/AHA Cholesterol Guidelines (Stone 2013) and patient's 10-year CV Risk Score (Goff 2013) will be considered.

Baseline Lipid and Lipoprotein Parameters:

- LDL-C (by tertile);
- HDL-C (by tertile, and tertile by gender);
- TG (by tertile, and tertile by gender);
- RLP-C (by tertile);
- TG \geq 150 mg/dL and TG <150 mg/dL;
- TG \geq 200 mg/dL and TG <200 mg/dL;
- TG \geq median, TG < median;
- combined highest tertile for TG and lowest tertile for HDL-C;
- gender-specific highest tertile for TG and lowest tertile for HDL-C;

- TG \geq 200 mg/dL with HDL-C \leq 35 mg/dL;
- hs-CRP (\leq 3 mg/L and $>$ 3 mg/L) and by gender;
- hs-CRP (\leq 2 mg/L and $>$ 2 mg/L) and by gender;
- Apo B (by tertile); and
- non-HDL-C (by tertile).

Adjustment for Baseline TG Level: Following a protocol amendment, dated May 2013, only patients with qualifying TG \geq 200 mg/dL were enrolled in the study. Prior to this, patients with qualifying TG levels as low as approximately 135 mg/dL were enrolled. In order to account and adjust for the fact the follow-up times may be different depending on the baseline TG level, a Cox PH model as mentioned above but additionally with baseline TG as a covariate will be fitted to the data at each interim. Diagnostic plots for the PH assumption will be evaluated.

The consistency of the treatment effects in subgroups will be assessed for the primary and key secondary efficacy endpoints. For each subgroup variable, a Cox proportional hazards model with terms for treatment, stratification factors (with the exception of those subgroup variables related to the stratification factors, i.e., CV risk category), subgroup, and treatment-by-subgroup interaction will be performed. The main treatment effect will not be tested with this model. P-values for testing the interaction terms $<$ 0.15 will be considered significant. Results will be presented in a Forest plot.

All subgroup analyses will be conducted for the ITT, mITT and PP populations.

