A Cox proportional hazard (PH) model as mentioned above but additionally with baseline TG as a covariate will be fitted to the data at each interim. Diagnostic plots for the PH assumption will be evaluated.

The consistency of the treatment effects in subgroups will be assessed for the primary and key secondary efficacy endpoints. For each subgroup variable, a Cox PH model with terms for treatment, stratification factors (with the exception of those subgroup variables related to the stratification factors, i.e., CV risk category), subgroup, and treatment-by-subgroup interaction will be performed. The main treatment effect will not be tested with this model. P-values for testing the interaction terms < 0.15 will be considered significant. Results will be presented in a Forest plot.

All subgroup analyses will be conducted for the ITT, mITT and PP populations.

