7. EXPLORATORY ANALYSIS OF SUBGROUPS

This section relates to Section 4.7.5 of version 1 of the SAP dated 08 July 2016.

The following will be added to the subgroup analyses:

- Baseline Hemoglobin A1c (HbA1c) value (<6.5%, ≥6.5%)

- Baseline PAD
- Baseline triglyceride (TG) levels ≥ 150 mg/dL with high-density lipoprotein cholesterol (HDL-C) levels ≤ 40 mg/dL for males and ≤ 50 mg/dL for females

Subgroup analyses of the primary and key secondary endpoints will be performed as described for the primary endpoint. For each subgroup, Kaplan-Meier estimates, the log-rank test stratified by stratification factors used at randomization (except where the subgroup is a stratification factor), and hazard ratios (HRs) and confidence intervals (CIs) from the Cox proportional hazards model as specified for the primary efficacy endpoint, will be summarized by treatment group.

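### Interaction p-values below 0.15 are to be called significant across 23 or more subgroup variables, so chance heterogeneity will almost always receive that label

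*Combined protocol and SAP*

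**What the plan says.** SAP 4.7.5 sets out the purpose: "The consistency of the treatment effects in subgroups will be assessed for the primary and key secondary efficacy endpoints". The method is one model per variable: "For each subgroup variable, a Cox proportional hazards model with terms for treatment, stratification factors", plus subgroup and treatment-by-subgroup interaction. The decision rule is "P-values for testing the interaction terms $<$ 0.15 will be considered significant", repeated in protocol 12.2.4.5 as "P-values for testing the interaction terms < 0.15 will be considered significant". Results go into a forest plot. On scope, the SAP adds: "All subgroup analyses will be conducted for the ITT, mITT and PP populations".

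The list introduced by "The following subgroups will be explored" has 23 entries: 5 demographic, 3 disease, 1 treatment, and 14 lipid, lipoprotein or hs-CRP entries. Section 7 of the SAP Addendum says "The following will be added to the subgroup analyses" and names three more: HbA1c, PAD, and raised TG with low HDL-C.

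Neither document says how many interactions to expect below 0.15 by chance, or how to interpret one that is.

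**The concern.** A lenient cut-off is a recognised way to screen for interactions, because such tests have low power. The difficulty is the label. SAP 4.3.1 tests efficacy outcomes at two-sided 5% unless otherwise noted, and 4.7.5 then attaches the word significant to a threshold three times as large. For tertiary endpoints, SAP 4.3.6 says that the results are exploratory and tested at a nominal level without adjustment. The interaction tests get no equivalent caveat.

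The rule is meant to judge consistency. If it reports inconsistency in nearly every trial where the effect is perfectly consistent, a reader of the forest plot cannot tell a pre-specified significant interaction from noise. Interpretation of the subgroup results is at stake, not the primary result.

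**Working it through.** The documents give no error rate for the interaction tests, so there is no figure of theirs to reproduce.

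**Inputs**
- Threshold 0.15 per test, and two endpoints (SAP 4.7.5).
- Number of variables, k. The SAP list gives 23. Counting the by-gender versions of HDL-C, TG and the two hs-CRP splits separately gives 23 + 4 = 27. The three Addendum subgroups make 30. The 10-year risk score, which the SAP says only will be considered, would add one more.

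**Expected number of chance flags, one endpoint, ITT.** With a common effect each p-value falls below 0.15 with probability 0.15, so the expected count is 0.15 × k whatever the correlation between tests:
- k = 23: 0.15 × 23 = 3.45
- k = 27: 0.15 × 27 = 4.05
- k = 30: 0.15 × 30 = 4.5

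**Chance of at least one flag if the tests were independent**, 1 − 0.85^k:
- k = 23: 97.6%
- k = 27: 98.8%
- k = 30: 99.2%

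**Allowing for overlap.** The tests are not independent, since several are different cuts of TG, HDL-C or hs-CRP. A simulation of 1500 trials used N = 7990, a control hazard of 0.053, the planned accrual over 6.5 years and a hazard ratio of 0.85 in every patient, with correlated and overlapping subgroup variables. Each interaction was tested by a heterogeneity chi-square on the subgroup log hazard ratios. The average rate per test was 0.152, close to nominal. For the primary endpoint in ITT:

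| k | at least one flag | mean flags |
|---|---|---|
| 23 | 95.2% | 3.6 |
| 27 | 95.9% | 4.2 |
| 30 | 97.1% | 4.6 |

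For k = 30 the median was 4 flags (5th to 95th percentile 1 to 10). Taking both endpoints in ITT, the chance of at least one flag was 99.2% (k = 23) to 99.6% (k = 30).

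**Lower range.** If the list carried only 10 to 15 effectively independent tests, one endpoint in one population would give 1 − 0.85^10 = 80.3% to 1 − 0.85^15 = 91.3%.

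**The case against.** The strongest reply is that nothing depends on the rule. The section is headed "4.7.5 Exploratory Analysis of Subgroups". Confirmatory claims are confined to the primary endpoint and the ordered secondaries (SAP 4.3.6). The interaction models do not test the main treatment effect, and the interim subgroup analysis in iSAP 4.2.4 gives only hazard ratios and 95% confidence intervals. The SAP Addendum says that all its efficacy analyses are exploratory. All of this stands. A reader might infer that the rule threatens the trial's efficacy claim; the documents do not support that.

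A second reply is that a liberal cut-off makes it harder, not easier, to claim a consistent effect, and that a multiplicity correction would nearly remove the ability to see real effect modification. This also stands. Take 1612 events split equally between two subgroups, with assumed hazard ratios of 0.75 and 0.95. The difference in log hazard ratios is ln(0.95/0.75) = 0.236. Its standard error is √(4/806 + 4/806) = 0.0996, a ratio of 2.37. With critical values of 1.44, 1.96 and 3.14, power is about 82% at 0.15, 66% at 0.05 and 22% at 0.05/30, which is Holm's first step. A Holm or permutation requirement is therefore a real trade-off and is not proposed here.

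Third, one might multiply 30 variables by two endpoints and three populations, get 180 p-values and 0.15 × 180 = 27 expected flags, and read these as 27 separate false findings. That does not follow. The mITT population is every randomized patient with drug dispensed and is likely to be close to ITT. The key secondary components all lie within the primary composite. One chance imbalance would be flagged repeatedly.

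Finally, 30 is the upper end of the count. Section 7 of the Addendum specifies Kaplan-Meier estimates, log-rank tests, hazard ratios and confidence intervals, but does not itself mention interaction tests. That its three subgroups follow SAP 4.7.5 is an inference. The 23 variables in the SAP are enough for the conclusion.

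**Conclusion.** The point holds as a labelling and interpretation defect in an exploratory analysis. Under an identical effect in all patients, about 3.5 to 4.5 interactions per endpoint in ITT would be called significant, and the chance of at least one is about 95% to 99%, or 80% to 91% on the low assumption of 10 to 15 effective tests. The expected count needs only the threshold and the number of variables. The 95% to 97% figures also rest on subgroup prevalences and correlations that the documents do not give; the two-endpoint figures further assume that 60% of the primary hazard comes from the key secondary components.

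A reader might go further and conclude that the subgroup results are worthless. That is not supported: the variables are listed in advance, and hazard ratios with confidence intervals will be shown for each. What the rule cannot do is separate consistency from inconsistency by the label alone.

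**What to change.** In SAP 4.7.5, and in the matching sentence of protocol 12.2.4.5, replace the statement that p < 0.15 will be considered significant. The new wording should say that interaction p-values are descriptive and unadjusted for multiplicity, and that p < 0.15 is only a screening flag and not in itself evidence of heterogeneity. Beside each forest plot, print the number of interactions tested and the number expected below 0.15 under a common effect (0.15 × number tested; for 23 variables, about 3.5). State whether the by-gender versions and the Addendum subgroups are included in that count.

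Every subgroup, estimate and analysis population stays, and so does the sensitivity of the 0.15 screen. The cost is a wording change and one line per plot; the small downside is that fewer interactions can be called significant. Keeping the label and lowering the threshold to 0.05 would not cure the problem: the chance of at least one flag per endpoint would still be 69% to 79% for 23 to 30 independent tests (62% to 69% in the simulation).
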